5.2 Study Population

We will select male participants with a body height corresponding to the average German body height of the working population aged 18-40 years old. We will recruit males only, because most assembly work at Audi is performed by men. In 2013, German males were on average 180.6 (SD 7.3) cm tall (Statistisches Bundesamt 2015).

5.3 In- and Exclusion Criteria

Inclusion criteria (Attachment 2):

- Age between 18 and 40 years;
- Male gender;
- The participant will give his voluntary informed consent after receiving oral and written information of the content and goal of the study.

Exclusion criteria (Attachment 2):

- Aged <18 and >40 years;
- Female gender;
- People under the influence of intoxicants, analgesics, or muscle relaxants;
- Alcohol abuse;
- People with cardiovascular diseases;
- People with a heart pacemaker;
- People with a disability who, due to their restriction at a workplace of this kind, will not be able to participate;
- People with Diabetes Mellitus;
- People with severe muscle contractions of the lower extremities, back or arms;
- People with acute ailments or pain;
- People who are unable to complete the examination program due to language or cognitive obstacles;
- Depending on the degree of severity, people with diseases of the veins and joints of the lower extremities, spine, muscle disorders, symptomatic neurological-psychiatric diseases, acute pain syndromes, maladies or other current diseases.

5.4 Recruitment

Volunteering participants will be recruited by means of an announcement e-mail at the University Hospital Tübingen, the Eberhard-Karls-University Tübingen, as well as by e-mail to former participants who agreed to be informed about future studies (Attachment 7).

[figure not shown]

Figure 2. Study course. During the exposure, posturography, muscle strain and work performance will be continuously recorded.

5.5 Sample Size

The planned study serves as a pilot study for a future larger research project and is intended to provide, among other things, the basis for a concrete calculation of the number of cases for follow-up projects. For this reason, and considering that we will include 7 experimental conditions with 3 working distances, we think that 21 individuals is the minimum for evaluating the exoskeleton, but we strive for 42 to have a double balanced randomization controlled cross-over design (double Williams Design). The total study population will be divided, based on body height, in three subgroups (Figure 2). The groups are based on (1) $< 25^{\text{th}}$ percentile, (2) 25^{th} to 75^{th} percentile, and (3) $> 75^{\text{th}}$ percentile of the average body height of 18-40 German males. As a result, the subgroup analyses may statistically be somewhat weaker than the overall statistical assessment of 42 participants.

We are mainly interested in recruiting men that fall in between the 25^{th} and 75^{th} percentile of the average German body height distribution, corresponding to Group 2 (Figure 2). The percentiles can be calculated using the formula: $X = \mu + Z \cdot \sigma$, in which μ is the population's mean, Z the z-value belonging to the desired percentile, and σ the population's standard deviation.

6 Study Procedure

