Since 2014, Audi has several passive exoskeletons to use in their production lines and factories in Southern Germany, where employees perform different types of assembly work while standing (Feigl 2015; Karius 2015; Stirnemann 2015). The passive exoskeleton, the 'Chairless Chair', provides support for the lower extremities. The system is developed by the Swiss company Noonee (Saameli 2014). The 'Chairless Chair' offers the potential for a reduction of awkward body postures, even in restricted spatial conditions at standing workplaces. It is unclear which physiological and

biomechanical loads are influenced by the 'Chairless Chair' exoskeleton and how. Furthermore, it is not clear whether participants of all body heights will experience the same beneficial effects, if any, when wearing the system.

3 Objectives

This research proposal aims to provide a sophisticated study design in which participants simulate assembly work related to that performed in the Audi factories. With measurements of several physiological and biomechanical parameters, work-physiological-biomechanical analyses will be performed to investigate the influence of wearing the exoskeleton during assembly tasks. The participants included will be grouped according to their body height, enabling us to investigate whether body height influences the effectiveness of wearing the exoskeleton.

4 Timetable

The project consists of four phases (Table 1). First, the study design and measurements need to be prepared, which will take approximately three months. Participants will be recruited during three months and the measurements will take up to three months. The data analysis, evaluation, writing and publication will be spread over five months. The four phases will be performed with some overlap with a total length of the study of about ten months.

Table 1. The timetable for the proposed study that will be completed early 2018.

5 Study Design and Study Population

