5.1 Study Design

The laboratory study will include several experimental conditions, being a combination of supported seating or unsupported standing by the exoskeleton, and three different working heights. These seven combinations will be offered to the subjects in a balanced, randomized cross-over design (Latin Square Williams Design; Williams 1949). In each of these seven conditions, three manual materials handling tasks will be simulated in a fixed order but in three different frontal working distances. Because of the three working distances, we will include a multiple of the 14 orders resulting from the Williams Design, striving for a population of 42 subjects.

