7.7 Participant Evaluation

When the participants have finished the experiment, we will provide them with a short questionnaire to report their opinion about using the exoskeleton for the various experimental conditions. This will provide us information about the acceptance of the worker regarding the use of the 'Chairless Chair'. The questionnaire will include items on feasibility, comfort, and usability (Attachment 6).

8 Statistical Analysis

When all data are collected, we will have a number of dependent variables as listed in Table 3. Each of these parameters will provide a(n) (average) value per condition, resulting in four values. For the continuous measurements, i.e. posturography, muscle strain, and work performance, we will average the values over each of the seven conditions. For the discontinuous measurements, i.e. subjective discomfort ratings, we will calculate the difference value of the pre- and post-condition measurements. Participant evaluations will not be tested but only discussed narrative.

Table 3. Summary of the model components that will be included in the statistical analyses.

Model component	Method / Name	Parameter
Dependent variable	Posturography	Center of Pressure (COP) Joint angles
	Muscle strain	Amplitude (ARV) Median power frequency (MdPF)
	Work performance	Error rate Timing error
	Subjective assessment	Rating of perceived discomfort (Borg RPE)
Within-subject factor	Working postures	Without, with (high), with (low) exoskeleton
	Working height	High, medium, low
	Working distance	Optimal, too far I, too far II
Between-subject factor	Group	Body height (S/M/L)

The current study has a repeated measures design including three within-subject factors (*exoskeleton*, *working height*, and *working distance*). If we have enough participants, we could also include a between-subject factor (*group*, based on body height), or another post-hoc identified discriminator. We will use a linear mixed effects model to perform the statistical analyses of all dependent variables (Table 3) using SPSS (IBM SPSS Statistics 23.0). This model allows observations to be not independent, because it adds a *random effect* for subject, i.e. modeled by assuming different *random intercepts* for each subject. This model also allows including both repeated measures, i.e. different conditions (within-subject factor: *working height*, *working posture*, *working distance*), and comparing independent groups of participants (between-subject factor: *group*).

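### Body height is recorded for every man but planned only as an optional three-level factor, which loses about a fifth of the linear information; separately, Section 5.5 understates how imprecise the height subgroups will be.

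*Combined protocol and SAP*

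**What the plan says.** - **Objective.** Section 3 says that the men will be grouped by height, "enabling us to investigate whether body height influences the effectiveness of wearing the exoskeleton".
- **Data.** Section 7.1 records body height, with age and weight, at the first visit.
- **Grouping.** Section 5.5: "The total study population will be divided, based on body height, in three subgroups (Figure 2". The groups are below the 25th, between the 25th and 75th, and above the 75th "percentile of the average body height of 18-40 German males". Section 5.2 supplies the distribution: "In 2013, German males were on average 180.6 (SD 7.3) cm tall".
- **Model.** Table 3 in Section 8 lists the between-subject factor as "Body height (S/M/L". No term in centimetres appears in the readable text. Section 8 makes the factor conditional on having enough participants.
- **Precision.** Section 5.5 concludes that "the subgroup analyses may statistically be somewhat weaker than the overall statistical assessment of 42 participants".
- **Sample size.** Section 5.1: "we will include a multiple of the 14 orders resulting from the Williams Design, striving for a population of 42 subjects". Section 5.5 adds "we think that 21 individuals is the minimum for evaluating the exoskeleton" and calls the study a pilot for a larger project. It also says that men in the middle height group are the main recruitment interest. The documents give no alpha, power, effect size or outcome SD.

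**The concern.** Cutting a measured covariate into three groups treats all men within a group as the same height. Here the middle group spans nearly 10 cm and would hold half of a population-like sample. The group-by-condition test also spends two degrees of freedom where a slope spends one. If height does modify the exoskeleton's effect roughly in proportion, the planned coding is less likely to show it and gives a later trial a less useful estimate.

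The precision remark in Section 5.5 is a different matter. It compares subgroups with the whole sample, not grouped with continuous height. A reader who takes it at face value could treat a finding of no difference between height groups as informative when it could easily reflect low power.

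**Working it through.** **Inputs from the documents.** Mean height 180.6 cm, SD 7.3 cm (5.2); cuts at the 25th and 75th percentiles (5.5); target 42, minimum 21 (5.1, 5.5).

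**Assumptions.** Normal heights; an effect linear in height unless stated; sample shares 25/50/25, that is 10.5/21/10.5 men (Figure 2, cited for the groups, is not shown); two-sided alpha 0.05. Each man contributes one condition contrast with between-subject SD 1.

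**Plan's own figure.** 14 Williams orders × 3 distance orders = 42; 7 × 3 = 21. Both reproduce. They come from design balance, not from a power calculation.

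**Cut-points.** Section 5.5's formula with z = ±0.6745 gives 180.6 ± 0.6745 × 7.3 = 175.7 and 185.5 cm.

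**Point 1: information lost by grouping.**
- Mean standardised height in an outer group: φ(0.6745)/0.25 = 0.3178/0.25 = 1.271.
- Share of height variance between groups: 0.5 × 1.271² = 0.808. The loss is 19.2%, so 42 men carry the linear information of 42 × 0.808 ≈ 34.
- Effect on the standard error of the height contrast: 1/√0.808 = 1.11, about 11% wider.
- The loss depends on the share of men in the middle group:

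| Middle share | Loss |
|---|---|
| one third | 16% |
| 50% | 19% |
| 60% | 22% |
| 70% | 26% |
| 80% | 33% |

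- Simulated power at n = 42. The linear effect has correlation 0.405 between height and the contrast, an assumed value chosen to give the slope roughly 80% power:

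| True pattern | Slope | Slope + quadratic | Three groups |
|---|---|---|---|
| Linear | 78% | 68% | 57% |
| Middle group differs by 1 SD | 5% | about 37% | 79% |

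**Point 2: precision relative to the overall analysis.**
- Overall effect: SE = 1/√42 = 0.154.
- Within an outer group: 1/√10.5 = 0.309, ratio √(42/10.5) = 2.0.
- Within the middle group: ratio √(42/21) = 1.41.
- Small minus large: √(2/10.5) = 0.436, ratio 0.436/0.154 = 2.8.
- The same short-versus-tall contrast (2 × 1.271 = 2.54 SD of height) from a continuous slope: 2.54/√42 = 0.392, ratio 2.5.
- Detectable at 80% power, (1.960 + 0.842) × SE: 0.43 SD overall, 0.86 SD in an outer group, 1.22 SD for small versus large, 1.10 SD for the same contrast from continuous height.
- With 70% in the middle group, each outer group has 42 × 0.15 = 6.3 men, and the small-versus-large ratio is √(2/6.3) × √42 = 3.7.
- At the minimum of 21, a 25/50/25 split leaves about 5 men in each outer group.

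**The case against.** **A stronger reading that fails.** A reader might infer that cutting height into groups is what makes the height question 2 to 2.8 times less precise than the overall analysis, and that using centimetres would cure it. The plan's own figures do not support this. Small outer groups and the between-subject nature of height account for most of the gap; continuous height moves the ratio only from 2.8 to 2.5. Nor can one say that a null result between height groups would mostly reflect the coding. In the linear scenario the miss rate rises from 22% to 43%, so coding accounts for about half of the misses under one assumed effect size that has no source in the documents.

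**Linearity.** The background in Section 2 questions whether men of all heights benefit equally, which is not necessarily a slope. Section 5.1.1 scales working height and distance to each man's anatomy, so a monotone trend is not the obvious alternative. A slope alone would almost never detect a middle-versus-extremes pattern (5% power against 79% for the groups). The quadratic term guards against this only in part, and it spends the second degree of freedom, which takes back about half of the power gain. This stands: neither coding dominates, so the groups should stay alongside the continuous term.

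**Status.** The factor is optional, the study is a pilot, and Section 5.5 does disclose that subgroup analyses are weaker. This also stands and limits the consequence. It does not remove the point, because the objective is stated without that condition and a slope with its interval would serve the planning of a later study.

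**Conclusion.** Both points hold, separately and at modest weight.

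1. Planning height only as an optional small/medium/large factor gives up about 19% of the linear information (range 16% to 33%) and widens the standard error of the height contrast by about 11%. This rests on normal heights, a linear effect and, for the central figure, population shares in the sample. If recruitment favours the middle group, as Section 5.5 intends, the loss is larger. A non-linear effect would change the comparison and could reverse it.
2. Section 5.5's description of subgroup precision is too mild. The ratios are about 2.0 within an outer group and 2.8 for small versus large under the assumed 10.5/21/10.5 split, and larger if the middle group dominates. The actual group sizes may be given in Figure 2.

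This is an inexpensive improvement to an exploratory analysis. It is not a flaw in the main comparison of conditions.

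**What to change.** **Section 8 and Table 3.** Add centred height (per 10 cm) and its interaction with working posture to the planned mixed model. Report the slope of the exoskeleton contrast on height with its 95% confidence interval, labelled exploratory. Add one quadratic term, with its interaction, to check for a non-monotone pattern. Keep the small/medium/large summaries alongside.

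**Section 5.5.** Replace the remark on subgroup precision with the expected ratios for the intended group sizes: about 2.0 within an outer group and 2.8 for small versus large at 10.5/21/10.5, and higher if the middle group is over-represented. Say that these arise mainly from small outer groups and the between-subject contrast, and that continuous height would still leave about 2.5.

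**Cost.** Wording in three places and one additional model per outcome; no new data. The downside is the linearity assumption. Checking it uses a second degree of freedom and brings power under a linear effect from 78% to 68%, still above the 57% for three groups.

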5.1.1 Independent variables (within-subject factors)

At first, experimental conditions are designed by a combination of working position and working height. We will investigate three different working positions [P]: (1) unsupported standing [US], (2) supported high seating [HS], and (3) supported low seating [LS]. We will investigate three working heights [WH]: high [H], medium [M], and low [L]. The combination of these two independent variables is displayed in Figure 1A. The randomized design for assigning conditions to subjects will be based on an orthogonal Latin Square Design (Figure 1B). A third independent variable considered is working distance, i.e. the distance of the task set-up from the front of the subject: (1) optimal, (2) far, (3) very far; the order of these three working distances will also be varied by assigning them balanced to the subjects. For the order of the three working distances, the outcome of a special type of Latin Square Design, the Williams Design suggests three different orders (for the complete experimental design, see Attachment 8).

A	WH _H	WH _M	WH _L	B	1	2	3	4	5	6	7	8	9	10	11	12	13	14
P_{SS}	V	V	X	1	A	B	C	D	E	F	G	D	E	F	G	A	B	C
P_{HS}	V	V	V	2	G	A	B	C	D	E	F	E	F	G	A	B	C	D
P_{LS}	X	V	V	3	B	C	D	E	F	G	A	C	D	E	F	G	A	B
				4	F	G	A	B	C	D	E	F	G	A	B	C	D	E
				5	C	D	E	F	G	A	B	B	C	D	E	F	G	A
				6	E	F	G	A	B	C	D	G	A	B	C	D	E	F
				7	D	E	F	G	A	B	C	A	B	C	D	E	F	G

A $P_{SS}WH_H$
B $P_{SS}WH_M$
C $P_{HS}WH_H$
D $P_{HS}WH_M$
E $P_{LS}WH_L$
F $P_{LS}WH_M$
G $P_{LS}WH_L$

Figure 1. A. Incomplete Block Design (Williams Design) based on position (P) and working height (WH), resulting in 7 different experimental conditions; B. Latin Square Design for 14 subject, which will be preferably elongated to a replicate of 14 subjects.

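### The readable plan does not say that condition orders are allocated within height group, and the Section 8 model has no period term, so session drift can add chance variance to the height-by-posture comparison (minor)

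*Combined protocol and SAP*

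**What the plan says.** - **Objective.** Section 3 groups participants by height, "enabling us to investigate whether body height influences the effectiveness of wearing the exoskeleton".
- **Groups.** Section 5.5: "The total study population will be divided, based on body height, in three subgroups (Figure 2". The cuts are the 25th and 75th percentiles for German men aged 18–40. The readable text gives no group sizes. It leans towards the middle group: "We are mainly interested in recruiting men that fall in between the" two cut points.
- **Orders.** Section 5.1: "we will include a multiple of the 14 orders resulting from the Williams Design, striving for a population of 42 subjects". The reason given for the multiple is the three working distances. For these, Section 5.1.1 says that "the Williams Design suggests three different orders" and that "the order of these three working distances will also be varied by assigning them balanced to the subjects". Balance is thus described over the subjects as a whole, and height group is not mentioned. The full list is referred to Attachment 8.
- **Minimum size.** Section 5.5: "we think that 21 individuals is the minimum for evaluating the exoskeleton".
- **Model.** Section 8 has posture, working height, working distance and a random intercept per subject. Height group enters only if there are enough participants. No period or sequence term is named.
- **Timing.** Section 6.1 gives about 20 minutes per condition and 3 minutes of rest. Height is recorded at the first visit (Section 7.1), and the order is used at the second (Section 6.1).

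**The concern.** The Williams square protects a posture contrast from session time because every condition falls equally often in every position. That protection holds for a complete set of orders. A height group that receives an arbitrary subset of orders may have its seated runs later, relative to its standing runs, than another group has. A change over the session that all men share, such as muscle fatigue or learning, then enters the short-versus-tall difference in the posture effect. Section 9 itself expects tension or fatigue as the experiment goes on. A random intercept removes a man's overall level but not a trend within his session.

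At stake is the precision of a stated objective in a study that is also meant to inform the sample size of follow-up projects.

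**Working it through.** **1. The plan's own figure.** Seven conditions give 2 × 7 = 14 Williams orders, and 14 × 3 distance orders = 42, the stated target. In Figure 1B each condition falls exactly twice in each position, and each ordered pair of conditions occurs exactly twice. Condition order is therefore balanced in every 14. The 42 completes the crossing with distance order. Columns 1–7 or 8–14 alone are balanced for position but not for carry-over.

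**2. Session length.** 20 + 3 = 23 min per period, and 7 × 23 = 161 min.

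**3. Timing gap per order.** For each column of Figure 1B: gap = mean position of the low-seat runs (F, G) minus mean position of the standing runs (A, B). Condition E, whose printed label repeats that of G, is not used. Example, column 2 (B A C G D F E): (6 + 4)/2 − (2 + 1)/2 = 3.5.

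The 14 gaps are 1, 3.5, 3.5, 1, −2.5, −4, −2.5, −1, −3.5, −3.5, −1, 2.5, 4, 2.5. Their sum is 0 and their sum of squares is 110, so SD = √(110/14) = 2.80 periods.

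**4. Group sizes (assumption).** Quartile cuts of 42 give 10.5 / 21 / 10.5 in expectation. I take 10 short and 11 tall men.

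**5. Imbalance if orders ignore height.** The 42 sheets hold each order three times, so the finite-population variance is 3 × 110/41 = 8.05. The tall-minus-short difference in mean gap has expectation 0 and

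SD = √[8.05 × (1/10 + 1/11)] = √(8.05 × 0.191) = 1.24 periods, or 1.24 × 23 ≈ 28.5 min.

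In simulation the absolute difference exceeds one period in about 42% of allocations. The same formula gives 1.07 periods for 14 versus 14 and about 1.8 for 5 versus 5. The last is roughly the minimum study of 21, treated as a draw from the 42-sheet list.

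**6. Effect on the contrast, without a period term.** Take residual SD 1 per condition and two runs per posture. The per-man contrast has variance 1/2 + 1/2 = 1, and the group difference has variance 1/10 + 1/11 = 0.191 (SE 0.437). A common linear drift of d residual SD per period adds variance d² × 1.24². The drifts are assumptions, since the documents give none.

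| d | Inflation 1 + (d × 1.24/0.437)² | If the posture effect also varies between men with SD 1 |
|---|---|---|
| 0.10 | 1.08 | 1.04 |
| 0.17 | 1.23 | 1.12 |
| 0.30 | 1.72 | 1.36 |

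In the last column the per-man variance is 2 instead of 1, so the excess is halved.

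**7. Effect of the remedies.**
- *Allocation within height group, least-used order first* (simulated with 10/21/11 men in random arrival): the SD falls from 1.24 to about 0.75 periods, and the share above one period from 42% to about 19%. With 14 men per group each group gets all 14 orders, and the gap is exactly zero.
- *Period as a fixed factor*: the shift from a common drift is zero whatever the allocation. The SE rises from 0.437 to about 0.448 for this contrast (2.5%). For all exoskeleton conditions versus standing, 10 versus 10 men, it rises from 0.374 to 0.379 (1.3%).

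**The case against.** **The documents are silent, not contrary.** A reader might infer that orders are known to be unbalanced within height groups. The text does not say so. Attachment 8 holds the full design and Figure 2 the groups, and neither can be seen here. This stands. The supportable statement is that the readable plan does not tie order to height group.

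**Balance does not need all 42.** A reader might infer from the target that it does. Step 1 shows that condition order is balanced in each 14. This also stands.

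**There is no systematic confounding.** Section 6.1 specifies a preset, balanced, randomized order. If it is assigned without regard to height, the expected imbalance is zero and only variance is added. The model's residual absorbs much of that: in a simulation with no true effect, no period term and 10 versus 11 men, type I error was about 5%, 6% and 7% at the three drifts (1,500 runs each). This stands too. Still, the study is run once, and the imbalance of its one allocation remains in its estimate.

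**Drift may be small.** Familiarization of 30 to 45 minutes and rest breaks limit learning and fatigue. Discomfort is analysed as a pre-to-post difference within each condition, which subtracts the accumulated level. This is fair, and it makes EMG, posture and performance the more exposed outcomes.

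**The comparison is optional.** Section 5.5 calls the study a pilot and already warns that subgroup analyses will be weaker. Section 8 makes the group factor conditional. This lowers the severity, but does not remove the point, because Section 3 states height as an objective.

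**Conclusion.** The point holds as a minor one. The readable plan neither allocates condition orders within height group nor models period, so a common session drift can add variance to the height-by-posture contrast. With 10 short and 11 tall men the chance imbalance has SD 1.24 periods. The resulting inflation is about 8% to 72% over drifts of 0.10 to 0.30 residual SD per period, and roughly half that if the posture effect varies between men as much as the residual.

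These sizes rest on assumed group sizes, an assumed linear drift common to all men, and orders assigned without regard to height. The documents do not support a claim of bias in a known direction, or of harm to the overall posture contrast, which stays balanced at 42.

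**What to change.** 1. **Sections 5.1 and 5.5, and Attachment 8:** state that orders are allocated within height group. Keep the same 42 sheets. Give each man an unused sheet whose condition order, then distance order, has been used least in his group. If Attachment 8 already does this, one sentence in Section 5.1 is enough.
2. **Section 8:** add period (1 to 7) as a fixed factor in the mixed model. This is the simpler safeguard, and it works even if recruitment leaves incomplete sets of orders. If drift may differ by height, period-by-group terms can be added. For all exoskeleton conditions versus standing, 10 versus 10 men, the SE is then 0.391 instead of 0.374, a rise of about 4.5%.

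The cost is one allocation list kept by height group and one more model factor, with a loss of about 1–3% in SE for period alone. No extra men, visits or measurements are needed, and the overall balance at 42 is kept.
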